4.2. Exclusion Criteria

Subjects presenting with any of the following will not be included in the present study.

1. Receipt of chemotherapy, immunotherapy, cryotherapy, radiotherapy, or anti-androgen therapy concomitantly, or within 8 weeks prior to screening visit, for treatment of Cancer of the prostate. Radiation for pain control will be allowed during the study.
2. Receipt of any vaccination (including influenza) within 4 weeks of screening visit
3. History of blood donation within 2 months of screening visit
4. History of anaphylaxis to any LH-RH analogues
5. Receipt of any LH-RH suppressive therapy within 6 months of screening visit
6. Patients who were previously enrolled in the LMIS 50 mg study
7. Major surgery, including any prostatic surgery, within 4 weeks of screening visit
8. History and concomitant clinical and radiographic evidence of central nervous system/spinal cord metastases and subjects at risk for spinal cord compression
9. Clinical evidence of active urinary tract obstruction and subjects at risk for urinary obstruction
10. History of bilateral orchiectomy, adrenalectomy, or hypophysectomy
11. History or presence of hypogonadism, or receipt of exogenous testosterone supplementation within 6 months of screening visit
12. Clinically significant abnormal ECG and/or history of clinically significant cardiovascular disease as judged by the investigator
13. History of drug and/or alcohol abuse within 6 months of screening visit
14. Contraindication to leuprolide or an LH-RH agonist as indicated on package labeling
15. Use of 5-alpha reductase inhibitor within the last 6 months of screening visit
16. History or presence of insulin-dependent diabetes mellitus (Type I). Presence of well controlled diabetes mellitus Type II will be allowed if only oral hypoglycemic are required. Prostate cancer subjects with poor controlled diabetes mellitus with Hb1Ac > 9.5% or urine glycosuria > 1.0 g/dL should be excluded.
17. Use of systemic corticosteroids at a dose > 10 mg/d or anti-androgens
18. Use of any investigational agent within 4 weeks of screening visit
19. Use of any over-the-counter (OTC) medication within 4 weeks of screening visit except for those listed in the permitted Concomitant Treatment section.

20. Uncontrolled intercurrent illness that would jeopardize the subject's safety, interfere with the objectives of the protocol, or limit the subject's compliance with study requirements, as determined by the investigator in consultation with the sponsor

4.3. Withdrawal Criteria

Discontinuation from study is defined as discontinuation of all study visits and examinations. Participants may voluntarily withdraw from the study for any reason at any time. They may be considered withdrawn if they state an intention to withdraw, or fail to return for visits, or become lost to follow up for any other reason.

Subjects will be withdrawn from the study if any of the following occurs during the study period, i.e. from screening visit to the end of study (EOS):

- (1) Lost to follow-up
- (2) Subject withdrew consent
- (3) In investigator's opinion that treatment with prohibited medications is needed
- (4) Adverse event/serious adverse event
- (5) Protocol violation (please provide specific reason)
- (6) Lack of efficacy as determined by investigator
- (7) Subjects with persistent, non-castrate serum testosterone levels (>50 ng/dL)
- (8) Other

Subjects who are withdrawn due to AEs or SAEs will be followed until these events are resolved or until the event is considered stable.

Should a subject's testosterone concentration be above the castration level (> 50 ng/mL) at or after Visit 9 (Day 28/week 4), an extra visit for confirmation of testosterone level will be issued immediately. Subjects will be withdrawn from the study at the time of confirmation from the repeat testosterone analysis. The investigators can provide other alternative treatments promptly to these withdrawn subjects in accordance with standard clinical practice.

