10.4.1. Analysis of primary endpoint

The primary endpoint of efficacy is to determine the percentage of subjects with a serum testosterone concentration suppressed to castrate levels (≤ 50 ng/dL) on Day 28 ± 1 day (week 4) following the first injection of LMIS 25 mg and to determine the proportion of subjects with serum testosterone suppression (≤ 50 ng/dL) from Day 28 ± 1 day (week 4) through Day 168 ± 5 days (week 24) until the end of the study.

The percentage of subjects with a serum testosterone concentration suppressed to castrate levels (≤ 50 ng/dL) on Day 28 ± 1 day (week 4) and on Day 168 ± 5 days (week 24) will be analyzed using a

Protocol No.: FP01C-17-001

standard large sample approximation to a Binomial distribution. The percentage of subjects with testosterone suppression (≤ 50 ng/dL) from Day 28 (week 4) through Day 168 ± 5 days (week 24) will be analyzed using the Kaplan-Meier approach.

Insufficient testosterone suppression is defined as suppression that does not occur by Day 28 (week 4) or occurrence of a testosterone level >50 ng/dL between Day 28 (week 4) and Day 168 (week 24).

The following efficacy analyses will be provided in detail in the statistical analysis plan:

- The proportion of subjects with testosterone suppression (≤ 50 ng/dL) from Day 28 (week 4) through Day 168 ± 5 days (week 24)
- Subjects exhibiting post-suppression breakthrough of serum testosterone to >50 ng/dL
- Time to event: A subject with a testosterone level > 50 ng/dL between Days 28 and 168 is considered to have an event.

To accommodate drop-out and missing values, the data censoring rules is shown in [Table 5](#).

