Yes	No	No	Censored on day of last measurement
Yes	No	Yes	Event on day of first escape
Yes	Yes	No	Censored on day of last measurement before the first missing
Yes	Yes	Yes	Event on day of first escape
No	No	No	Censored on Day 168
No	No	Yes	Event on day of first escape
No	Yes	No	Censored on day of last measurement before the first missing
No	Yes	Yes	Event on day of first escape
No suppression by Day 28			Event on Day 28

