1. INTRODUCTION

This is a multi-national, multi-center, open-label, single-arm and phase III study to determine the efficacy, safety, and pharmacokinetic profile of LMIS 25 mg in patients with prostate cancer. Approximately 133 subjects will be enrolled in this study.

This statistical analysis plan (SAP) is based on protocol version 1.1, dated 20-Nov-2017. The SAP provides details of data handling procedures and statistical analysis methods for efficacy and safety evaluations. It also outlines statistical programming specifications for tables, listings and figures, and other details on the analyses not provided in the study protocol. It is noted that in case there is discrepancy between the SAP and the protocol then the SAP will supersede the protocol.

This SAP will include efficacy and safety analysis only. The pharmacokinetic (PK) analysis plan is not part of this SAP.

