9. EFFICACY ANALYSIS

9.1 Primary Efficacy Variable

The primary endpoint of efficacy is to determine the percentage of subjects with a serum testosterone concentration suppressed to castrate levels (≤ 50 ng/dL) on Day 28 ± 1 day (week 4) following the first injection of LMIS 25 mg and to determine the proportion of subjects with serum testosterone suppression (≤ 50 ng/dL) from Day 28 ± 1 day (week 4) through Day 168 ± 5 days (week 24) until the end of the study.

The percentage of subjects with a serum testosterone concentration suppressed to castrate levels (≤ 50 ng/dL) on Day 28 ± 1 day (week 4) and on Day 168 ± 5 days (week 24) will be analyzed using a standard large sample normal approximation to a Binomial distribution and it will be summarized as count, percentage and exact 95% CI for binomial proportion.

The percentage of subjects with testosterone suppression (≤ 50 ng/dL) from Day 28 (week 4) through Day 168 ± 5 days (week 24) will be analyzed using the Kaplan-Meier approach. In this analysis an event is defined as occurring in subjects with a testosterone level > 50 ng/dL between Day 28 (week 4) and Day 168 (week 24). To accommodate drop-out and missing values the following censoring rules will be observed:

Table 9.1-1 Data Censoring Rules

Subject Discontinued	Day 28- 168 or Day of Discontinuation		To Be Handled As
	More Than 1 Missing Testosterone Value	Any Escape*	
Yes	No	No	Censored on day of last measurement
Yes	No	Yes	Event on day of first escape
Yes	Yes	No	Censored on day of last measurement before the first missing

Statistical Analysis Plan

Yes	Yes	Yes	Event on day of first escape
No	No	No	Censored on Day 168
No	No	Yes	Event on day of first escape
No	Yes	No	Censored on day of last measurement before the first missing
No	Yes	Yes	Event on day of first escape
No suppression by Day 28			Event on Day 28

*The escape (event) is defined as subject with a testosterone level >50 ng/dL

The testosterone level will be listed by subject and visit in [Listing 16.2.6.1](#).

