The subject with PSA relapse is defined as after achieving the serum PSA level ≤ 4 ng/mL post LMIS 25 mg injection but with an increase in serum PSA of $>50\%$ PSA nadir by Day 168 (week 24), i.e. subject achieves the serum PSA level ≤ 4 ng/mL on Day 28 but with an increase in serum PSA of $>50\%$ PSA on Day 84 or Day 168, or subject achieves the serum PSA level ≤ 4 ng/mL on Day 84 but with an increase in serum PSA of $>50\%$ PSA on Day 168.

The incidence of PSA relapse will be presented as subject count, percentage, and exact 95% CI for binomial proportion in [Table 14.2.8](#) and [Table 14.2.20](#) for ITT and PP populations; and the percentage of subject achieves normal serum PSA level will be presented as [Table 14.2.9](#) and [Table 14.2.21](#) for ITT and PP populations. Besides, the additional analyses of PSA levels <4 ng/mL for subjects with elevated PSA at baseline as [Table 14.2.11](#) and [Table 14.2.23](#). It is noted that the normal serum PSA level shall be analyzed as <4 ng/mL rather than <4 ng/dL since it is typo on protocol.

- The percentage of subjects with enhanced serum testosterone concentration suppression to ≤ 20 ng/dL on Day 28 ± 1 day (week 4) and on Day 168 ± 5 days (week 24)

The percentage of subjects with a serum testosterone ≤ 20 ng/dL on Day 28 ± 1 day (week 4) and on Day 168 ± 5 days (week 24) will be analyzed using a standard large sample normal approximation to a Binomial distribution. The summary results included subject count, percentage and exact 95% CI for binomial proportion will be presented as [Table 14.2.10](#) and [Table 14.2.22](#) for ITT and PP populations.

Based on protocol, the testosterone level is assessed at Week 26 for the first enrolled 30 subjects. The additional analysis of subjects with a serum testosterone concentration suppressed to castrate levels (≤ 50 ng/dL) at Week 26 will be presented as [Table 14.2.12](#) and [Table 14.2.24](#) for ITT and PP populations.

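### Protocol 4.3 prints the trigger for the confirmatory testosterone visit in ng/mL instead of ng/dL, which makes it 100 times the castrate limit

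*Protocol*

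**What the plan says.** Protocol section 4.3 lists the reasons for withdrawal and then gives a procedure. Should a subject's "testosterone concentration be above the castration level (> 50 ng/mL) at or after Visit 9" (Day 28), "an extra visit for confirmation of testosterone level will be issued immediately". Withdrawal follows once the repeat analysis confirms the result, and the investigator may then start other treatment promptly.

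Item (7) of the same list gives the limit in a different unit: "Subjects with persistent, non-castrate serum testosterone levels (>50 ng/dL".

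The rest of the plan agrees with item (7):

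- Protocol 10.4.1 defines insufficient suppression as failure to suppress by Day 28 or "occurrence of a testosterone level >50 ng/dL between Day 28 (week 4) and Day 168 (week 24".
- The footnote to SAP Table 9.1-1 reads "The escape (event) is defined as subject with a testosterone level >50 ng/dL".
- The synopsis and the primary endpoint in Protocol 2.2.1 also put the castrate level at 50 ng/dL or below.

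The SAP does notice a unit slip elsewhere in the protocol. Section 9.2 says that the "normal serum PSA level shall be analyzed as <4 ng/mL rather than <4 ng/dL since it is typo on protocol". It says nothing about the testosterone trigger.

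**The concern.** The mis-stated number is in an instruction that sites act on. The sentence sets off an immediate visit, then withdrawal on confirmation, then a change of treatment for a man whose cancer therapy is not suppressing testosterone. No other section describes this step. The synopsis repeats the list of withdrawal reasons but not the confirmatory visit. Item (7) requires the non-castrate level to be persistent without saying how persistence is shown, so the faulty sentence is the only guide on that.

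Taken literally, the instruction would hardly ever apply, and a subject who had escaped could wait longer for his repeat test. Deviation review would also become awkward. Under item 2 of Protocol section 16, failing to withdraw a subject who met a withdrawal criterion is reportable, yet a site following the printed number would have had no reason to order the repeat test.

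**Working it through.** **Inputs**

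- Printed trigger: above 50 ng/mL (Protocol 4.3, procedure after the list).
- Castrate limit: 50 ng/dL (Protocol 4.3 item 7; Protocol 2.2.1 and 10.4.1; SAP Table 9.1-1 footnote).
- Entry floor for testosterone before treatment: above 150 ng/dL (Protocol 4.1 item 4).
- Metric conversion: 1 dL = 100 mL, so 1 ng/mL = 100 ng/dL.

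**Conversion**

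- Printed trigger in ng/dL: 50 × 100 = 5,000 ng/dL.
- Castrate limit in ng/mL: 50 / 100 = 0.5 ng/mL.
- Ratio of printed trigger to castrate limit: 5,000 / 50 = 100.
- Ratio of printed trigger to entry floor: 5,000 / 150 = 33.3.
- Range in which a value is non-castrate but does not exceed the printed trigger: above 50 and up to 5,000 ng/dL, a width of 5,000 − 50 = 4,950 ng/dL.

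The printed figure therefore does not match the castration level that the sentence says it represents. With the unit changed to ng/dL it matches exactly.

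**Does the SAP repair it?** SAP section 1 says that "in case there is discrepancy between the SAP and the protocol then the SAP will supersede the protocol". That helps only where the SAP has a rule of its own. The SAP contains no confirmatory-visit rule, so there is nothing to take precedence.

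**Does it reach the primary analysis?** In Protocol Table 5 and SAP Table 9.1-1, every row with an escape is handled as "Event on day of first escape", and lack of suppression by Day 28 is an event on Day 28. Neither rule asks for confirmation or refers to the section 4.3 trigger. The success criterion in SAP 9.1 (lower 95% confidence bound above 90%) is applied to the resulting suppression rate at Day 168. The sample-size inputs (null 0.90, alternative 0.97, n = 120) are proportions and do not depend on the unit.

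**How many subjects?** The documents give no escape rate for the 25 mg dose, so no count can be derived. For scale only, if the planning assumption of 97% success held, about 0.03 × 133 = 4 subjects would exceed 50 ng/dL at some point from Day 28. In the earlier 50 mg study, four of 137 did not have successful suppression (Protocol 1.3).

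**The case against.** The strongest reply is that this is a typing error that corrects itself. The sentence names the castration level, item (7) gives that level a few lines earlier, and the rest of the plan agrees. An investigator who manages hormone therapy would read 50 ng/dL. Protocol 7.2.1 also lets investigators order extra testosterone tests whenever they wish, and item (6) allows withdrawal for lack of efficacy, so a prompt repeat does not depend on this sentence. The SAP had reason to fix the PSA unit, because that is an analysed endpoint. It had no such reason for a visit instruction it does not use. Finally, SAP 4.4 already reports 144 subjects enrolled, so a correction may come too late to change much at sites.

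All of this is fair, and it is why the point is minor. It does not make the printed threshold correct. A discretionary test is not a required one, and the required one carries the wrong number.

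Two further objections limit what may be claimed:

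- That the printed trigger would practically never be met is an assumption. The documents give no upper range for testosterone. They show only that 5,000 ng/dL is 33.3 times the entry floor.
- The statement that the primary analysis is untouched is shown directly for the Kaplan-Meier part. The Day 168 percentage, also listed under the primary endpoint, uses subjects with a value at that visit, and missing values are not imputed (SAP 5.2). Whether an escaped subject was withdrawn could therefore in principle decide whether he is counted there. Item (7) requires withdrawal for persistent values either way, so this route is theoretical.

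**Conclusion.** The concern holds, as a minor point. The trigger in Protocol 4.3 is wrong as printed by a factor of 100 (5,000 against 50 ng/dL), and no other text in the protocol or SAP states the confirmatory step correctly. The effect is confined to the site instruction for the immediate repeat test. Withdrawal for persistent values above 50 ng/dL still stands under item (7), and the Kaplan-Meier event rule, the censoring rules and the sample size are unaffected.

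The error and its size follow from the documents and the metric conversion alone. The practical consequence depends on whether any site applied the unit literally, and the documents do not show that.

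**What to change.** In Protocol 4.3, change the unit of the trigger from ng/mL to ng/dL by a protocol clarification letter. The PSA unit slip that the SAP already notes can be corrected in the same letter.

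As an optional check, compare Listing 16.2.6.1 (testosterone by subject and visit) with Listing 16.4.9 (unscheduled assessments) to see whether subjects above 50 ng/dL from Day 28 onward had a repeat test. Read the result with care. Samples to the Bioanalytical Lab are batched, and the additional Central Lab tests are routinely no more than monthly (Protocol 7.2.1), so a late or absent repeat does not show that the unit was taken literally. The SAP also does not say outright that repeat testosterone results will appear in Listing 16.4.9, so confirm that first. Sites that followed the printed unit should not automatically be charged with a deviation.

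The cost is one unit in one sentence. Both listings are already planned. The endpoint definition, the design, the sample size and the SAP analysis need no change.

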6.22. Visit 22 (Day 168 ± 5 days/EOS/ ET; week 24)

The following procedures and sample collection should be performed at this visit:

1. Conduct physical examination (including body weight) and record vital signs.
2. Perform ECG.
3. Collect blood sample for analysis of the following:
 - Hematology: CBC, such as Hb, Hct, RBC count, WBC count, WBC differential and platelet count
 - Biochemistry: ALT, AST, ALP, total bilirubin, BUN, Serum Cr, electrolytes (K, Na, Mg, Ca and P), blood glucose, lipid profile (LDL, HDL, triglycerides)
 - HbA1c
 - PSA level
4. Collect urine sample for urinalysis:
 - pH, specific gravity, leukocyte, erythrocyte, protein, urine glucose, and nitrate
5. Collect serum sample for pharmacokinetics of leuprolide mesylate.
6. Collect serum samples for testosterone and LH.

Protocol No.: FP01C-17-001

7. Assess bone pain.
8. Assess urinary signs and symptoms.
9. Record concomitant medication(s).
10. Record AE(s).
11. Exit off the study (for the 103 subjects without extended PK follow up).
12. For early termination subjects, phone contacts should be performed at 12 weeks after the last injection of investigational product to collect drug-related AE, concomitant medication or non-drug therapy received for AE treatment, disease progression status, and subject survival status.

Subjects who withdraw from the study prematurely for any reason during the study period will undergo the assessments listed for the final End of Study (EOS)/Early Termination (ET) visit. If a subject refuses to return for these assessments or is unable to do so, every effort should be made to contact him or a knowledgeable informant by telephone to determine his condition. Documentation of attempts to contact the subject should be recorded in the medical chart and CRF.

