8.2. Prohibited Treatment

The following medications are prohibited during the study period (from screening visit to EOS):

1. Other gonadotropin-releasing hormones
2. Other chemotherapy, immunotherapy, cryotherapy, or radiotherapy for treatment of prostate cancer
3. Any OTC medication other than those listed in the Concomitant Treatment section.
4. Dietary supplements, herbal supplements, or herbal tea.
5. Insulin
6. Anti-androgens
7. 5-alpha reductase inhibitors
8. Systemic corticosteroids > 10 mg/d

Subjects who have received these prohibited treatments will be withdrawn from the study.

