16. PROTOCOL DEVIATION / VIOLATION

All deviations from the protocol should be reported to QPS. This includes, but is not limited to, the following:

1. Subjects who entered the study but did not satisfy all entry criteria;
2. Subjects who satisfied the criteria for one or more of the withdrawal reasons during the study but were not withdrawn;
3. Subjects who received the wrong treatment or incorrect dose;
4. Subjects who received concomitant treatment in an incorrect manner or who received a non-approved concomitant treatment.
5. Subjects who missed the sample collection for efficacy assessment on the scheduled visit

Examples include subject noncompliance with medication, surreptitious use of medications prohibited by the protocol, inability, or unwillingness to accurately report AEs or concomitant medication use. Additionally, exceptions or deviations that could conceivably affect the collection or interpretation of the data related to safety or efficacy assessments should also be reported.

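### Protocol 4.3 stops scheduled sampling after a confirmed escape; the SAP's by-visit breakthrough formula then drops these failures, and its Day 168 castrate percentage has no rule for them

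*Protocol*

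**What the plan says.** **Withdrawal.** Protocol 4.3 sends any man above castrate at or after Visit 9 (Day 28) for an immediate repeat. If the repeat confirms the value, "Subjects will be withdrawn from the study at the time of confirmation from the repeat testosterone analysis". The same section states: "Discontinuation from study is defined as discontinuation of all study visits and examinations". It lists persistent non-castrate levels as a withdrawal reason (item (7): "Subjects with persistent, non-castrate serum testosterone levels (>50 ng/dL"). The sentence with the trigger prints ng/mL; I take ng/dL, as in item (7), to be meant. There is no exemption after Day 84, the last dosing day. Protocol 16 includes among reportable deviations: "Subjects who satisfied the criteria for one or more of the withdrawal reasons during the study but were not withdrawn".

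**What remains.** Protocol 6.22 provides one final set of assessments: "Subjects who withdraw from the study prematurely for any reason during the study period will undergo the assessments listed". These include testosterone. A phone contact 12 weeks after the last injection collects no testosterone. On treatment after withdrawal, 4.3 says: "The investigators can provide other alternative treatments promptly to these withdrawn subjects in accordance with standard clinical practice".

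**Analysis.** In the Kaplan-Meier analysis (Protocol Table 5, SAP Table 9.1-1) an escape is an event on its first day, whether or not the man discontinues. SAP 9.1 divides by-visit breakthrough by the men castrate at Day 28 who have a non-missing testosterone value at that visit. For the Day 28 and Day 168 castrate percentages it says only: "it will be summarized as count, percentage and exact 95% CI for binomial proportion". SAP 5.2 imputes no missing efficacy data unless otherwise specified.

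**The concern.** A man leaves the sampling schedule because he failed on the variable being summarised. His absence from later visits is therefore informative, and a table restricted to men with a value will look better than the treated group really is. Two summaries are exposed:

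- **By-visit breakthrough.** The formula is explicit, and following it removes confirmed failures at every visit after withdrawal.
- **Day 168 castrate percentage.** The SAP fixes neither the denominator nor the status of these men nor the use of an early ET value. The analyst could drop them, count them as failures, or carry their ET value to Day 168.

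Both summaries are supportive, but they appear among the SAP's primary efficacy tables in an open-label, single-arm trial. The choice should not be left until the data are seen.

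**Working it through.** **The plan's own figure.** The plan gives no figure for this point. Its sample-size statement (n = 120, 0.90 against 0.97, one-sided 0.025, 85% power) reproduces by exact binomial: success at 115 or more of 120, power 84.7%. This point does not affect it.

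**Samples lost.** The scheduled testosterone days after Day 87 are 98, 112, 140, 161 and 168, which is 5 samples. The first 30 men also have Days 126 and 182, which makes 7. A man confirmed before Day 98 loses all of these except his ET sample. Days 85, 86 and 87 are largely kept, because a result and a repeat must come back before he is withdrawn.

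**How many men.** The only data in the documents are from the 50 mg study (Protocol 1.3), which used a different dose and a 6-month depot. I scale to the 144 men enrolled (SAP 4.4), with exact Clopper-Pearson intervals.

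- Excursions after the second dose: 2/137 = 1.46% (0.18% to 5.17%). Times 144, this is 2.1 men (0.3 to 7.5). Both were transient, so a repeat might not have confirmed them.
- Persistent escapes after the second dose: 0/137 (upper limit 2.66%). Times 144, this is 0 men (upper limit 3.8).
- Not castrate at Day 28: 137 - 135 = 2, so 2/137 and again about 2 of 144. These men are outside the breakthrough denominator, so they matter for Day 168 only.

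That gives about 0 to 2 men after Day 84, plus up to about 2 Day 28 failures for the Day 168 percentage.

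**Day 168 percentage.** I assume 10% ordinary dropout (144 x 0.9 = 129.6, taken as 130 men who would otherwise have a value), every other man castrate, and the lost men still non-castrate.

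| Men lost | Counted as not castrate | Observed cases | Gain | All 144 as denominator |
|---|---|---|---|---|
| 1 | 129/130 = 99.2% | 129/129 = 100% | 0.8 points | 129/144 = 89.6% |
| 2 | 128/130 = 98.5% (94.6% to 99.8%) | 128/128 = 100% (97.2% to 100%) | 1.5 points | 128/144 = 88.9% |
| 4 | 126/130 = 96.9% (92.3% to 99.2%) | 126/126 = 100% | 3.1 points | 126/144 = 87.5% |

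The gain is zero if the lost men had recovered, if a non-castrate ET value is taken as Day 168, or if all 144 men form the denominator.

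**By-visit breakthrough.** Two men lost while still escaping: 2/130 = 1.5% (0.2% to 5.5%) becomes 0/128 = 0% (0% to 2.8%).

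**Kaplan-Meier.** Each of these men is already an event, on the day of first escape or on Day 28. Withdrawal changes nothing.

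**The case against.** Every confirmed escape is already in the primary analysis. One found at a scheduled visit is also in the breakthrough rate at that visit, and the listings show the values and the reason for discontinuation. Table 14.2.1 is labelled ITT, and where the SAP wants observed cases it says so, so the inflating reading of Day 168 is not the obvious one. Ordinary dropout matters more: with the same 128 castrate men, changing the denominator from 130 to 144 moves the rate from 98.5% to 88.9%, or 9.6 points. Counting withdrawn men as not suppressed also assigns a status at visits with no measurement. Most of this stands and limits the point to a minor one. It does not rescue the breakthrough formula, whose denominator is explicit and removes men because they failed.

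Stronger readings that the documents do not support:

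- **The primary result is biased.** It is not: an escape is an event whether or not the man discontinues. The success criterion mentions a response rate at Day 168, but it directly follows the Kaplan-Meier summary and belongs to that estimate.
- **The SAP has no by-visit rule.** It has one; the fault is in what the rule does.
- **Nothing is measured after withdrawal.** The ET sample and the phone contact remain.
- **Protocol 4.3 should be amended to keep sampling these men.** The case is weak. They may move promptly to another treatment, and later values would then reflect that drug. Agents prohibited in Protocol 8.2 carry their own rule ("Subjects who have received these prohibited treatments will be withdrawn from the study"). Days 85 to 87 are largely kept, bioanalytical samples are shipped in batches, and 144 men are already enrolled.

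**Conclusion.** The point holds as a minor one. Following the plan understates breakthrough at visits after a confirmed escape, and SAP 9.1 leaves the status of these men in the Day 168 percentage open. The likely size is about 1.5 points for two men. It would be about 3.1 points if two post-dose escapers and two Day 28 failures were all lost, and it may be nothing at all. Taking the upper limit for transient excursions would give seven men (123/130 = 94.6% against 100%, 5.4 points). That is an extreme bound, because the repeat test is there to screen such excursions out.

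These sizes rest on three assumptions: that the 50 mg study is a fair guide to this product, that dropout is near 10%, and that lost men were still non-castrate. The Day 168 effect also needs an observed-case denominator, which the SAP neither states nor excludes.

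**What to change.** Edit SAP 9.1 only:

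1. In the by-visit breakthrough percentages, keep each man who was castrate at Day 28 and later withdrawn for confirmed escape in the denominator at visits after withdrawal, and count him as not suppressed.
2. In the Day 168 castrate percentage, keep every man withdrawn for confirmed escape, including Day 28 failures, in the denominator as not suppressed.
3. Count an ET value as Day 168 only if it falls within Day 168 ± 5, that is Days 163 to 173.
4. State the Day 168 denominator, including how other dropouts are treated.
5. Show the observed-case figures alongside.

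The Kaplan-Meier event stays on the day of first escape. SAP 5.2 allows a stated exception to its no-imputation rule, so nothing else in the plan has to change. No amendment to Protocol 4.3 or 8.2 is needed.

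The cost is a few sentences and one extra row per table. The downside is a slightly less favourable Day 168 rate: if two withdrawn men had in fact recovered, the rule reports 128/130 = 98.5% where full sampling would have given 130/130 = 100%. The observed-case row lets a reader see that difference.
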